**4.1.4. As applicable, provide information on any added protections for vulnerable populations.**

*N/A*

**4.1.5. If applicable include information on data and specimen banking.**

*N/A*

**5. Recruitment Methods**

**5.1. State how many subjects will be needed.**

*64 subjects*

**5.2. Describe when, where, how and by whom potential subjects will be identified and recruited.**

*Eligible Veterans will be identified through data-base review of eligibility. The study team will reach out to the Veteran's provider to ensure they agree with recruitment, and then the*

Veteran will be mailed a recruitment letter with study information and an invitation to participate. The letter will also notify potential participants that they will be telephoned by the project coordinator and will offer them the opportunity to refuse this contact by calling an answering machine and leaving a message. The project coordinator will telephone all patients who do not "opt out". Five attempts will be made by telephone. During screening phone call, inclusion/exclusion criteria will be confirmed. Study visits will be scheduled same day as clinical appointments when possible.

5.3. **Describe materials that will be used to recruit subjects, e.g., advertisements.**  
**Include materials as an appendix or separate attachment**  
A recruitment letter will be used, as noted above in 5.2.

5.4. **Describe any payments to subjects, including the amount, timing (at the end of the study or pro-rated for partial study participation), method (e.g., cash, check, gift card), and whether subjects will experience a delay in receiving the payment.**  
Participants will be compensated \$50 for the baseline questionnaire, \$5 per biweekly survey (up to 18 times over 9 months) and \$25 per quarterly survey (up to 4 times over 9 months). Participants can be compensated up to \$2400 total incentive. Patients will be paid via voucher or check from the VA.

## 6. Informed Consent Procedures

6.1. **Indicate if informed consent will be obtained and/or if you are requesting a waiver of informed consent or waiver of documentation of informed consent. If the research involves multiple phases, specify for which phases of the research the waiver(s) is being requested and/or the informed consent will be sought.**  
Informed consent will be obtained. We will be obtaining an oral informed consent in part due to limitations as a result of COVID19. This is due to risks of obtaining in person consent for both patients and study staff. The patient will be contacted via telephone or VA Video Connect for the consent process, and the informed consent form will be read aloud to the participant to ensure full understanding of the purpose of the study, study procedures, as well as the risks and benefits of participating. Once the study coordinator confirms through questioning that the participant fully understands all aspects, oral consent will be documented. A copy will be mailed to the patient and be placed in the patient's chart.

6.2. **Describe who will be obtaining informed consent, if applicable, and any circumstances that may need to be addressed (e.g. subjects with impaired decision making ability and the use of a legally authorized representative, etc.)**  
Study staff, such as the PI or the project coordinator will obtain informed consent.

6.3. **If applicable, indicate how local site study personnel will be trained regarding human subjects' protections requirements and how to obtain and document informed consent.**  
All study staff will be trained/overseen by PI. All study staff will have completed relevant training regarding human subjects protection and how to obtain informed consent. All personnel are required to have CITI (Good Clinical Practices and Ethical Principles), VA Privacy and Information Security Awareness and Rules of Behavior, and Privacy and HIPAA Trainings. In addition, all study staff obtaining informed consent will have taken the VA Research Compliance Officer training.

## 7. Inclusion/Exclusion Criteria

7.1. **Describe the criteria that determine who will be included in or excluded from the study.**  
Inclusion criteria for Veterans will be primary care patients who are dispensed ≥84 consecutive days of a stable dose of opioids (reflecting three consecutive 28-day

prescriptions) through primary care and who report stable levels of pain intensity over the past month. Patients will also need to have a smartphone with the ability to download a mobile application.

Exclusion criteria will be Veterans on liquid methadone or buprenorphine for opioid use disorder (OUD) and those who have transitioned to buprenorphine (transdermal or sublingual) for chronic pain, have hearing or visual impairments (not corrected with hearing aids or glasses), psychiatric conditions, cognitive impairments, or participating in a concurrent pain or opioid-related research study.

## 8. Study Evaluations

8.1. Describe all evaluations to be conducted (including screening; tests/questionnaires that will be administered; any procedures that subjects will be required to complete) and data collection methods. Include materials as an appendix or separate attachment.

The following questionnaires will be delivered through REDCap by the study coordinator at the outset of the study, and then every 6 weeks over the course of the study: Baseline Assessment, Daily Opioid Dose, Prescribed Opioids Difficulties Scale, PHQ-8, GAD-7, Modified Social Support Survey, Change Questionnaire, BIRS-24, PROMIS-29 Profile v2.0, and WHO 5-Item Well Being Scale. Participants will complete the surveys with the study coordinator, who will enter the responses into REDCap.

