### 2. Indicate how the PHI will be obtained by checking one or more of the boxes below:

- From existing sources such as medical records, clinical databases, or research records.

If the above box is checked, specify each source and who maintains the database:

Database Name	Who Maintains the Database
Corporate Data Warehouse	VA
CPRS Medical Charts	VA

*Additional rows may be added as required.*

- Directly from project participants during protocol procedures as described elsewhere in this application or in the protocol.

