#### 4. Study Procedures

##### 4.1. Study Design

4.1.1. Describe experimental design of the study. Include sequential and/or parallel phases of the study, including durations, and explain which interventions are standard of care.

*The study design is a 9-month, randomized, 2-arm, parallel, open-label feasibility trial. Eligible participants will be randomized to a brief single Motivational Interviewing (MI) session and SUMMIT versus a pain monitoring app. All participants will also be provided a referral to speak with a clinical pharmacy specialist about their medications and options for tapering. Feasibility and outcomes planned for a full-scale RCT will be collected at one-, three-, six-, and nine-months post-randomization. Opioid dose and adverse events (AEs) will be collected bi-weekly. We will send the link to the questionnaire to the participant if they have given permission to contact via email, otherwise we will send them the link via text, or read it aloud to them. Given the urgency to develop effective programs to support tapering efforts, we will perform interim analyses at three months. If positive, results of these analyses would expedite onset of the planned full-scale RCT.*

*Eligible patients on long term opioid treatment (LTOT) or on buprenorphine will be identified through VA Corporate Data Warehouse (CDW). Receipt of opioid medication will be defined as any dispense of a VA formulary category CN101 drug. Veterans having liquid methadone dispensed in the previous six months will be excluded. Because all methadone for the treatment of OUD is dispensed at federally licensed opioid treatment programs, we will cross check all methadone dispenses with stop code 523, the code used exclusively in those programs. For Veterans who remain eligible, a focused electronic medical record (EMR) review will be conducted to determine whether the Veteran is currently receiving liquid methadone or participating in a concurrent pain or opioid-related research study, and to check for evidence of hearing or visual impairments (not corrected with hearing aids or glasses), cognitive impairment or psychiatric condition. A list of eligible Veterans will be compiled into an Excel file and saved on the secured CHERP server. This list of potential subjects will NOT be printed out.*

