## 9. Data Analysis

9.1. Provide sample size determination and analysis (include anticipated rate of screen failures, study discontinuations, lost to follow-up etc.).

The calculated number of participants to be enrolled in this feasibility study was based on the approach outlined by Cocks and Torgerson (85), which recommends using a 1-sided confidence interval (CI) to determine whether it is worthwhile proceeding with a full-scale trial. If the proportion of participants achieving the primary outcome is 20% or lower in the control group (14), the sample size required to detect a difference of 15% in the main trial (assuming 80% power, alpha = 0.05, two-sided test) is 276. (14, 85) A pilot sample size of 48 would produce a one-sided 90% CI that would exclude finding a 15% difference in the larger fully-powered trial. To account for the reasonably high drop-out rate, we will inflate the sample size by 25%. Thus, we will randomize 64 participants.

9.2. Describe how, where and by whom the data will be analyzed.

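### Follow-up opioid dose is listed only as participant self-report in an open-label trial, although the VA dispensing records that define eligibility could supply a second dose measure

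*Combined protocol and SAP*

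**What the plan says.** **How dose is measured in follow-up.** Section 16, 8.1 lists "Daily Opioid Dose" among the REDCap questionnaires given at the outset and every six weeks, and states that "Participants will complete the surveys with the study coordinator, who will enter the responses into REDCap". Section 16, 4.1.1 has dose and adverse events collected every two weeks and names no source. Section 9 (item 2.2) and Section 16, 5.4 pay participants for up to 18 two-weekly surveys, so the two-weekly dose is most naturally read as survey data as well.

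**Survey mode.** Section 16, 4.1.1 says that a questionnaire link goes to the participant by email or text, or is read aloud, and that surveys are emailed through REDCap. The abstract (Section 14) also has assessments completed electronically.

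**Dispensing data.** For eligibility, 4.1.1 states: "Receipt of opioid medication will be defined as any dispense of a VA formulary category CN101 drug". Section 16, 7.1 requires at least 84 consecutive dispensed days at a stable dose. Section 11, item 2 names the "Corporate Data Warehouse" and the CPRS charts as sources of health information, and Section 3 ticks chart review as a method. No section takes follow-up dose from either source.

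**Use of dose.** Under Section 16, 9.2 the three-month interim analysis looks at recruitment, use of SUMMIT and opioid dose reduction, and its results may bring forward the full-scale trial.

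**The concern.** Entry is defined by dispensed dose and change by reported dose, with no planned link between the two. The trial is open-label, and only the experimental arm has a motivational interview and a program aimed at tapering. A participant who knows this may overstate a reduction, and that error would favour the experimental arm. Survey dose is also lost when participants stop answering. The plan expects considerable drop-out, and those who stop may differ in how far they tapered.

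At stake is the only clinical signal in the interim analysis. A second stake is what the pilot teaches: 9.2 says its data will decide which measures go into the full-scale trial, and a survey-only pilot cannot show how self-reported and dispensed dose compare. Because 4.1.1 leaves tapering steps to the participant's own provider or the clinical pharmacy specialist, a real taper should show in the prescriptions filled.

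**Working it through.** **1. The plan's own figures (Section 16, 9.1).** Inputs: "If the proportion of participants achieving the primary outcome is 20% or lower in the control group"; "the sample size required to detect a difference of 15% in the main trial (assuming 80% power, alpha = 0.05, two-sided test) is 276"; "A pilot sample size of 48 would produce a one-sided 90% CI that would exclude finding a 15% difference"; and "To account for the reasonably high drop-out rate, we will inflate the sample size by 25" per cent, giving 64 randomised 1:1.

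- Main trial, 20% against 35%, mean 27.5%: n per arm = [1.960·√(2·0.275·0.725) + 0.8416·√(0.20·0.80 + 0.35·0.65)]² / 0.15² = (1.2377 + 0.5239)² / 0.0225 = 137.9, so 138 per arm and 276 in total. This agrees with the plan.
- Pilot, 20% in both arms, 24 per arm: one-sided 90% half-width = 1.2816·√(2·0.20·0.80/24) = 1.2816·0.1155 = 0.148, or 14.8 points. This is below 15, and 48 is the smallest even total that achieves it.
- Drop-out: 48/(1 − 0.25) = 64. Read literally, an increase of 25% would give 48·1.25 = 60. The 64 is right for a 25% loss, so only the wording is loose.

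The point therefore rests on no arithmetic error.

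**2. What the expected loss leaves open.** Suppose 24 of 32 are observed in an arm and 20% of them achieve the outcome, that is 4.8 participants. If none of the 8 missing achieved it, the arm's rate is 4.8/32 = 15%. If all did, it is 12.8/32 = 40%. That 25-point range is wider than the 15-point target difference. It is an extreme bound, not a forecast.

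**3. What dispensing data could recover.** Section 16, 10.2 ends all collection at formal withdrawal, so only loss through survey non-response is recoverable. The documents give no withdrawal rate, so the rates below are assumptions. The formula is 1.2816·√(0.32/n per arm), with 20% in both arms and a dose-based binary outcome.

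| Formal withdrawal (assumed) | Evaluable of 64 | n per arm | Half-width |
|---|---|---|---|
| 0% | 64 | 32 | 1.2816·0.1000 = 12.8 points |
| 5% | 60.8 | 30.4 | 1.2816·0.1026 = 13.1 points |
| 10% | 57.6 | 28.8 | 1.2816·0.1054 = 13.5 points |
| 15% | 54.4 | 27.2 | 1.2816·0.1085 = 13.9 points |
| 25% (nothing recovered) | 48 | 24 | 1.2816·0.1155 = 14.8 points |

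**4. Passages side by side.**

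- Mode: completed with the coordinator, who enters the answers (8.1), against a link sent to the participant, with reading aloud as the fallback (4.1.1), and electronic completion (Section 14).
- Interval for dose: every six weeks (8.1) against every two weeks (4.1.1, Section 14).
- Motivational interview: a study coordinator (4.1.1) against a co-investigator (Section 16, 1.2, item 7).

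In either mode the dose comes from a participant who knows the arm. No masked assessor is described, and none could mask a self-report.

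**The case against.** **Dose is reported to the person who counselled the participant.** A reader might infer this from 8.1 together with the interview description in 4.1.1. The documents do not support it as the plan: other passages send the surveys to the participant, and 1.2 gives the interview to a co-investigator. What stands is self-report by an unmasked participant, a weaker route to bias.

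**Silence is not exclusion.** Sections 4.1.1 and 14 name no source for the two-weekly dose, chart review is a ticked method, and the warehouse is not expressly limited to screening. This is fair. The plan does not rule out dispensing data. It just never plans them for outcome, and the payment schedule points to surveys.

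**Dose is the primary outcome.** This is tempting, but the documents never define the primary outcome of the planned trial. The half-widths above apply to dose only if that outcome is dose-based.

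**Dispensing data would give all 64 participants.** That needs zero formal withdrawals, and 10.1 also withdraws participants diagnosed with opioid or substance use disorder. The 12.8-point figure is a best case.

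**The loss is overstated and changes no decision.** Section 9.2 plans models with participants as random factors, so those who drop out still contribute earlier observations, and the complete-case calculation does not measure the gain in that model. The 14.8 points already meet the 15-point criterion, most analyses are descriptive, and response rates and missing data are themselves results of the pilot. All of this stands. It limits the precision argument. It does not touch reporting bias, or the need to know how the two measures compare before the larger trial.

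**Dispensing has its own errors.** It measures supply, not intake. It may miss non-VA fills, and with 28-day prescriptions it is coarser than two-weekly reports, notably at month 1. This also stands, and is why it should be added and not substituted.

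**Conclusion.** The point holds as an inexpensive improvement the sponsor should make. It invalidates none of the plan's stated conclusions. Follow-up opioid dose, the only clinical measure in the interim analysis, is listed only as self-report in an open-label trial where one arm is counselled to taper, while the dispensing data that define eligibility have no planned outcome use.

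A dispensed-dose measure is free of survey-reporting bias and recovers the part of the 25% loss due to survey non-response. The size of the bias cannot be derived from the documents. The precision gain is roughly 1 to 1.7 points on the one-sided 90% limit (14.8 − 13.9 = 0.9; 14.8 − 13.1 = 1.7). It assumes a dose-based binary outcome, 20% in both arms, 5% to 15% formal withdrawal, and all remaining loss being survey non-response. The gain under the planned repeated-measures model is not calculable from what is given.

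Separately, the conflicts on survey mode and dose interval need resolving whether or not the measure is added.

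**What to change.** 1. In Section 16, 8.1, keep the survey item and add a dispensed daily dose derived from the Corporate Data Warehouse at baseline and months 1, 3, 6 and 9, for every randomised participant who has not formally withdrawn. State the derivation rule in advance, including how fills and days of supply become a daily dose.
2. In 9.2, analyse it with the same model as self-reported dose and report the two side by side, with the completeness of each.
3. In 9.2, state before enrolment which source feeds the three-month dose trend.
4. Reconcile 8.1 with 4.1.1 and Section 14 on survey mode and dose interval, and 1.2 with 4.1.1 on who delivers the interview.
5. Record the limits: dispensed is not consumed, non-VA fills may be missed, and 28-day fills are coarser than two-weekly reports.

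**Cost.** One further extract from a source already in use, some programming, and consent and HIPAA wording. The wording needs care: the waiver in Section 7 covers recruitment only, and the consent and authorization text that would govern outcome extracts is not among the documents available here. No change in sample size is needed.

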## 9. Data Analysis

9.1. Provide sample size determination and analysis (include anticipated rate of screen failures, study discontinuations, lost to follow-up etc.).

The calculated number of participants to be enrolled in this feasibility study was based on the approach outlined by Cocks and Torgerson (85), which recommends using a 1-sided confidence interval (CI) to determine whether it is worthwhile proceeding with a full-scale trial. If the proportion of participants achieving the primary outcome is 20% or lower in the control group (14), the sample size required to detect a difference of 15% in the main trial (assuming 80% power, alpha = 0.05, two-sided test) is 276. (14, 85) A pilot sample size of 48 would produce a one-sided 90% CI that would exclude finding a 15% difference in the larger fully-powered trial. To account for the reasonably high drop-out rate, we will inflate the sample size by 25%. Thus, we will randomize 64 participants.

9.2. Describe how, where and by whom the data will be analyzed.

Quantitative statistics will be performed by SAS, version 9.4. and will be performed by [name] (PI) and [name] (co-I). As we are proposing a feasibility trial, most of the analyses are descriptive. We will use descriptive characteristics to describe the study population, all feasibility outcomes, and the distribution of the primary and secondary outcomes planned for the full-scale trial. We will ascertain the distributional characteristics, response rates as well as the percent of the missing data for all baseline and follow-up measures at each time point. Although not powered to detect significant between-group, we will compare differences in the primary and secondary outcomes to examine preliminary trends that may inform the design of the full-scale trial. We will use regression analyses to examine the association between group assignment and the primary and secondary outcomes. Group assignment and time will be modeled as fixed factors and participants as random factors. Separate models will be conducted for each outcome. We will perform an interim analysis at three months to evaluate trends in the recruitment rate, use of SUMMIT, and opioid dose reduction. These results may support earlier initiation of the planned full-scale RCT. Exploratory mediation analyses will be used to examine the processes underlying change. We will use the product of coefficients method to determine whether 1) "dose" (amount of use with specific SUMMIT components) and 2) change in specified theoretical constructs mediate the relationship between treatment assignment

and clinical outcome measures. (86) We will also examine the effect of compliance on change in theoretical constructs and the primary and secondary outcome measures using a Complier Average Causal Effect analysis. (87) To examine heterogeneity, exploratory moderating analyses will be performed by including an interaction term (moderator X intervention status) in a multiple linear regression model. We will construct separate models for the following five possible moderators: age, baseline opioid dose, duration of LTOT, prevalent comorbid mental illness, and baseline intrinsic motivation. Although we will not be sufficiently powered to perform definitive mediation or moderating analyses, the data generated from this feasibility study will determine which measures to include in the full-scale trial.

10. **Withdrawal of Subjects**

10.1. **Describe any anticipated circumstances under which subjects will be withdrawn from the research without their consent.**

Subjects diagnosed with opioid use disorder (OUD) or substance use disorder (SUD) during the study will be withdrawn and referred for treatment. The study team will notify their PCP if this is the case. Subjects exhibiting inappropriate behavior online or with a peer specialist may also be withdrawn.

10.2. **Describe the consequences of a subject's decision to withdraw from the research and the procedures for orderly termination of participation by the subject (e.g., the subject contacting the investigator for an end-of-study visit).**

No consequences for withdrawal. Once we are notified of a participant's decision to withdraw, we can continue to use information about them that has been collected up to that point. No information will be collected after a participant formally withdraws.

11. **Reporting**

11.1. **Include procedures for reporting unanticipated problems, serious adverse events, and protocol deviations.**

Protocol deviations, unanticipated/unexpected problems will be reported to the IRB within 5 business days of discovery. We will use the CMCVAMC serious-adverse event form for reporting SAEs, UADEs, and any other unanticipated/unexpected problems. We will also use the CMCVAMC Protocol Deviation form for reporting any protocol deviations. Any adverse event would be reported to the IRB at continuing review. Further, if the patient develops any concerns with their medication treatment plans, particularly effects related to their opioid tapers, these will be referred to their PCP.

12. **Privacy and Confidentiality**

12.1. **Describe whether the study will use or disclose subjects' Protected Health Information (PHI).**

For Veterans, we will need to obtain name, date of birth, complete mailing address, race, gender, and medical history. This information will be used only in our analysis and to contact the Veteran (mailing address); no information will be disclosed to others outside our study team. The applications being used by the study, likewise, will not use or disclose the participants PHI.

12.2. **Describe the steps that will be taken to secure the data (e.g., training, authorization of access, password protection, encryption, physical controls, Certificates of Confidentiality, and separation of identifiers and data)**

All study personnel will complete the required human subjects, HIPAA, and information security and privacy trainings at the VA. All paper/hard copy data, which includes subject log, informed consent forms, HIPAA authorization forms, and surveys will be maintained in study binders. The study binders in CMCVAMC will be kept in CHERP, [name] in a locked file cabinet. Any electronic data, which includes the subject log and the key linking participants to their ID number at CMCVAMC will be kept on the secured CMCVAMC server vhaphicherpnas (\vhaphifpccherp.v04).

*med.va.gov\shares2\[name]). The log and the key will be kept in separate folders on the server and will NOT be printed out. Study personnel with access to study data and who are no longer involved with the study will have access revoked and will be removed from the research staff form.*

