*The study team will reach out via email to the primary care providers of Veterans who remain eligible after the above screening, to ensure the provider agrees with approaching the Veteran for possible enrollment.*

*Approved Veterans will then be mailed a letter informing them of the purpose of the study. The letter will notify potential participants that they will be telephoned by the project coordinator and will offer them the opportunity to refuse this contact by calling an answering machine and leaving a message. The project coordinator will telephone all patients who do not "opt out." If someone other than the participant answers the telephone, no personal health information (PHI) will be shared with the person who answers. Five attempts will be made to make contact with the potential participants. Veterans may also be informed of the opportunity to participate in the study by their primary care provider and be provided with a study letter. The study team will contact the Veteran within a week of provision of study letter. Participants will be assured that their participation is voluntary and that they can opt out from participating. During the telephone call, the remaining eligibility criteria will be verified.*

*Up to 64 patients will be recruited to participate in this research study. Due to COVID19, participants will undergo the informed consent process over the telephone, and provide oral consent.*

*All participants will be offered a referral to a clinical pharmacy specialist in the pain clinic to discuss options for medication management and opioid tapering. As part of the informed consent, patients will be reassured that the tapering steps will be conducted by their own pain care provider or with the assistance of the clinical pharmacy specialist.. After obtaining consent, participants will be trained on how to complete baseline and outcome measures on their preferred device. **Surveys will be sent to the participant via email through RedCap. As an alternative, we will register participants into the VA HealtheDialog text messages system in order to receive surveys and access the SUMMIT web application via link.** Baseline measures will be completed during this visit, prior to randomization, to ensure that participants are comfortable completing surveys electronically.*

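### For continuous outcomes, the between-group model in 9.2 omits the pre-randomization baseline value as a covariate and so gives up precision that the pilot could have at almost no cost

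*Combined protocol and SAP*

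**What the plan says.** Section 16, 9.2 states the model for primary and secondary outcomes, one model per outcome: "Group assignment and time will be modeled as fixed factors and participants as random factors". It names no covariate and no group-by-time term. The only interaction in 9.2 belongs to the separate moderator analyses, which proceed by "including an interaction term (moderator X intervention status) in a multiple linear regression model". Baseline values appear in a model only there, in the list of moderators: "age, baseline opioid dose, duration of LTOT, prevalent comorbid mental illness, and baseline intrinsic motivation".

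The baseline data will exist and are suitable as covariates. Section 16, 4.1.1 says: "Baseline measures will be completed during this visit, prior to randomization". On follow-up, the same section says: "Feasibility and outcomes planned for a full-scale RCT will be collected at one-, three-, six-, and nine-months post-randomization". It also has opioid dose collected bi-weekly.

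9.2 describes most of the analyses as descriptive and says the study is not powered for between-group differences. The purpose of comparing the groups is to "examine preliminary trends that may inform the design of the full-scale trial". Other planned outputs are distributions, response rates and the "percent of the missing data for all baseline and follow-up measures at each time point", and a three-month look to "evaluate trends in the recruitment rate, use of SUMMIT, and opioid dose reduction".

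**The concern.** In a small trial the participant's own baseline value is usually the strongest predictor of a continuous outcome such as a questionnaire score or opioid dose. A model with group, time and a participant effect does not use it to explain variation between people, and it lets any chance imbalance at baseline pass into the group difference. The loss matters more when few participants are analysed.

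9.2 also leaves open how baseline otherwise enters. It could be left out, be subtracted to form a change score, or be entered as one more response row. The last choice would pull the group term towards zero, because randomized groups do not differ in expectation at baseline.

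A lesser matter is that main effects of group and time give one group difference averaged over the modelled visits. That number is the same whether the effect holds, grows or fades. The descriptive summaries and the three-month look do not supply a modelled group difference with an interval at each assessment.

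**Working it through.** **The plan's own figures (9.1).** Comparing 20% with 35%, two-sided alpha 0.05, power 80%, pooled-variance formula without continuity correction: 138 per arm, 276 in total. Pilot: 1.2816 × √(2 × 0.2 × 0.8 / 24) = 0.148, just inside 0.15, so 24 per arm and 48 in total. Dropout: 48 / (1 − 0.25) = 64. All three reproduce, and none uses the 9.2 model.

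**Inputs from the documents.** Four follow-up assessments (4.1.1), 48 analysable participants and hence 24 per arm, 64 randomized, 25% dropout (9.1). **Assumed:** a continuous outcome with SD 1 at every visit and the same correlation r between any two measurements.

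**Variance per person of the quantity compared, k = 4 visits.** With balanced data and a random participant effect, the group coefficient is the difference in person-means.

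- Raw follow-up average: u = (1 + 3r)/4
- Average change from baseline: u + 1 − 2r
- Baseline-adjusted average: u − r²
- SE of the group difference: √(2v/24)

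| | r = 0.5 | r = 0.7 | r = 0.8 |
|---|---|---|---|
| Raw variance | 0.625 | 0.775 | 0.850 |
| Change-score variance | 0.625 | 0.375 | 0.250 |
| Adjusted variance | 0.375 | 0.285 | 0.210 |
| Cut against raw | 40% | 63% | 75% |
| Cut against change score | 40% | 24% | 16% |
| SE raw (SD units) | 0.228 | 0.254 | 0.266 |
| SE change score | 0.228 | 0.177 | 0.144 |
| SE adjusted | 0.177 | 0.154 | 0.132 |
| SE adjusted, one visit, v = 1 − r² | 0.250 | 0.206 | 0.173 |

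At r = 0.3 the raw variance is 0.475 and the adjusted variance 0.385, a cut of 19%.

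**Sensitivity.** With 32 per arm and 8 per arm leaving, equally likely before any of the four visits (12,000 simulations), the cuts at r = 0.5/0.7/0.8 are 38/62/74% against raw and 38/23/14% against change scores. If the correlation is a × b^(months apart), with (a, b) = (0.70, 0.97), (0.80, 0.95) or (0.85, 0.93), it falls from about 0.7–0.8 with baseline at month 1 to about 0.4–0.5 at month 9. The cuts are then 52/55/53% against raw and 31/29/31% against change scores.

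**Baseline as a response row.** With k follow-up rows and one baseline row, a constant effect appears as k/(k + 1) of its size: 4/5 = 80% for four visits, 6/7 = 86% for six, 18/19 = 95% for eighteen.

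**What the average cannot show.** Visit effects of 1, 1, 1, 1 (steady), 0.21, 0.63, 1.26, 1.89 (growing, in proportion to 1, 3, 6, 9 divided by their mean 4.75) and the reverse of that (fading) all give a group coefficient of 1.0.

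**The case against.** A reader might infer that the model cannot meet its stated purpose because a single averaged term shows no trend. The documents do not support that. The purpose is attached to comparing differences between groups, and 9.2 uses the same word for recruitment rate, so the natural meaning is the direction of an effect rather than its course over time. An average over follow-up is a legitimate target in an unpowered pilot and is more precise than any one visit. Group differences by visit are therefore extra reporting, not the repair of an error.

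A reader might also infer that baseline will be a response row and shrink the effect to 80%. 4.1.1 points the other way, since it describes outcomes as collected after randomization. The 80% also holds only for four follow-up rows. It is a reason to state the response rows, not evidence of bias.

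The sentence in 9.2 is brief, and a covariate or interaction may have been intended; silence is not exclusion. The correlations are assumed. The largest cuts apply against raw scores, while the phrase about opioid dose reduction may suggest change scores, where at r = 0.8 the SE moves only from 0.144 to 0.132. 9.1 treats the primary outcome as a proportion, to which none of these figures applies.

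All of this limits the size and rank of the point. What it leaves standing is that no part of the plan puts the baseline value into the between-group model, and that adjusting lowers the variance in every scenario examined.

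**Conclusion.** The point holds as a loss of precision for continuous outcomes, under the model as written. For the averaged difference over four visits, baseline adjustment removes 40% to 75% of the variance against raw scores and 16% to 40% against change scores at r from 0.5 to 0.8. These sizes rest on assumed correlations and a common SD; only the visits, 48, 64 and 25% come from the documents. The gain is worth having because the data are already being collected.

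The inability to tell a steady effect from a changing one follows from the model's form and needs no assumed correlation, but it supports only a secondary, descriptive addition. The comparison is exploratory, no decision stated in the plan depends on this coefficient, and the sample size is unaffected.

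**What to change.** In Section 16, 9.2, for continuous outcomes, state that:

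- the responses are post-baseline values, so that baseline is not a response row;
- the fixed effects are group, time and the participant's own baseline value of that outcome, with participant as random;
- the main result is the baseline-adjusted average group difference with its interval, over visits that are named;
- as a secondary, descriptive analysis, group-by-time is fitted with categorical time at the scheduled 1-, 3-, 6- and 9-month assessments only, and the four differences are shown with intervals and noted as less precise than the average.

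Restricting the last item matters. Bi-weekly opioid-dose records could otherwise yield up to 18 unpowered contrasts in about 48 people.

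The cost is a few sentences in 9.2 and a few lines of SAS, with no new data, visits or participants. The assessment schedules in 4.1.1 (1, 3, 6 and 9 months) and 8.1 (every 6 weeks) must be reconciled separately, since they determine which time levels the model contains.
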